10.1 Determination of Sample Size

The FLT3-3 D835 AML activating mutations have been refractory to currently available TKIs. An upper one-sided 75% confidence bound on the fraction of such patients who might respond to no treatment or ineffective therapy is 10%.

Therefore we will treat 15% response rate as our null hypothesis and submit 14 patients to this phase II trial. If at least 2 patients respond to treatment, the null hypothesis will be rejected. If the true response rate is 30%, this design will have 85.07% power and 8.61% type I error.

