The modeling/simulation cycle described above was performed with combined data from two adult studies (19 patients, ARO-BRE-001 (NCT01229644) and 002 (NCT01243346)) and one pediatric study ARO-003 (NCT01393912). This data was used to perform distribution of the BSA-normalized crenolanib pharmacokinetic parameters and the expected distribution of BSA in an adult population to perform 1,000 Monte Carlo simulations for each regimen. In figure 8.1, the shaded regions represent the 95% CIs for each simulation. The patients' dosing interval is considered to be every eight hours. Although the drug would be administered three times a day on a "TID" schedule, it is important to understand that the simulation was performed using an every eight hour dosing schedule and every attempt should be made to dose the drug on this schedule.

[figure not shown]

Figure 8.1. The PK simulation for TID (median +/- SD) plotted based on a simulation of data from 19 adult patients and pediatric patients.

The serum PK results of the 16 AML patients enrolled to date at 100mg TID across two clinical studies show that fifteen have cycle 1 day 15 average trough levels of 444nM (standard error ±15nM), below the theoretical target of 680nM required to inhibit FLT3 signaling in bone marrow. In addition, the Pk data suggest that crenolanib is slowly absorbed with a t-max of 2-4 hours and mean terminal half-life ranging from 8.6-9.5 hours. This suggests the currently administered crenolanib dose of 100mg TID (protocol v3) is insufficient to achieve adequate sustained inhibition of FLT3 kinase activity. As of May 2013, of the 16 patients enrolled across two clinical studies, 4 have achieved a CR (1CR/3CRi) with 6 others having some short lived reduction in blast cells in either blood or marrow and another 4 patients showing no response. In the 6 patients with blast decrease, blast reduction occurred by 21 days but was not sustained. These results suggest pharmacologic failure for most patients at this initially selected dose of 300mg/day (100mg/TID). In addition, AML patients over 85kg did not achieve sustained responses and are potentially underdosed on a flat-dose schedule.

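### Passing the 2-of-14 rule can support activity at most, not improvement of version 4 dosing over 100 mg TID, whose reported 4/16 response rate would itself pass 89.9% of the time

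*Combined protocol and SAP*

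**What the plan says.** Section 10.1 takes its benchmark from patients not given effective treatment: "An upper one-sided 75% confidence bound on the fraction of such patients who might respond to no treatment or ineffective therapy is 10"%. It then uses a higher null: "Therefore we will treat 15% response rate as our null hypothesis and submit 14 patients to this phase II trial". The decision rule is "If at least 2 patients respond to treatment, the null hypothesis will be rejected", and the stated properties are "If the true response rate is 30%, this design will have 85.07% power and 8.61% type I error".

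Section 8.6, in the same version, gives results for the earlier flat dose. As of May 2013, "of the 16 patients enrolled across two clinical studies, 4 have achieved a CR (1CR/3CRi"). On the pharmacokinetic data it concludes: "This suggests the currently administered crenolanib dose of 100mg TID (protocol v3) is insufficient to achieve adequate sustained inhibition of FLT3 kinase activity". On the clinical results it says: "These results suggest pharmacologic failure for most patients at this initially selected dose of 300mg/day (100mg/TID"). The new BSA-based dose is offered there as a way to reduce such failure.

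Section 10.1 does not mention the section 8.6 results. Sections 10.3, 10.3.6 and 10.3.7 plan a binomial test, descriptive statistics by best response, and Kaplan-Meier summaries. None of them compares response with the earlier dose or splits response by dosing regimen.

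Sections 7.1 and 8.7 allow patients enrolled under version 3 to stay at 100 mg TID or move to the new scheme. Section 10 does not say whether those patients are among the 14.

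**The concern.** Version 4 changed the regimen because the sponsor judged 100 mg TID inadequate. A reader of the final report will naturally ask whether the new regimen did better, and will look to the primary test for the answer. The test is set against inactive therapy, and its bar is low enough that a regimen performing exactly like the earlier one would usually clear it. Two responders of 14 is 14.3%, below both the 15% null and the earlier 25%, yet it would count as rejection.

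If patients who started on 100 mg TID count among the 14, the rule could be met partly or wholly by responses at the earlier dose. A positive result would then say nothing about version 4 dosing.

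**Working it through.** **Inputs.** From section 10.1: n = 14, reject at 2 or more, null 15%, alternative 30%, stated type I error 8.61%, stated power 85.07%. From section 8.6: 4 CR/CRi among 16 patients, so 4/16 = 25%. The text gives counts, and the percentage is derived here.

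**Formula.** For a cutoff of 2, P(X ≥ 2) = 1 − (1 − p)^n − n·p·(1 − p)^(n − 1). Higher cutoffs use the corresponding exact binomial tail.

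**Step 1: the plan's own figures.** With n = 14:
- p = 0.15: 1 − 0.1028 − 0.2539 = 0.6433
- p = 0.30: 1 − 0.0068 − 0.0407 = 0.9525

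The rule as written has 64.3% type I error and 95.3% power, so the stated figures are not reproduced. A search over other sample sizes, cutoffs and rates found one match to both, namely 2 or more of 10 with a 5% null and a 30% alternative:
- p = 0.05: 1 − 0.59874 − 0.31512 = 0.0861
- p = 0.30: 1 − 0.02825 − 0.12106 = 0.8507

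**Step 2: the section 8.6 rate.** With n = 14 and p = 0.25: 1 − 0.0178 − 0.0832 = 0.8990.

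**Step 3: separating the cutoff from the null.** The pass probability depends on the cutoff and the true rate. The null enters only through the choice of cutoff. For n = 14:

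| Cutoff | True 15% | True 25% | True 30% |
|---|---|---|---|
| ≥ 2 (as written) | 64.3% | 89.9% | 95.3% |
| ≥ 4 | 14.7% | 47.9% | 64.5% |
| ≥ 5 | 4.7% | 25.9% | 41.6% |

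Five is the smallest cutoff that keeps error at 15% below 10%. So the 89.9% is caused by the cutoff of 2. Raising the null without moving the cutoff would leave it unchanged. A cutoff valid for 15% still passes a 25% regimen about one time in four, because it tests a different question.

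**Step 4: uncertainty in the 25%.** The exact (Clopper-Pearson) 95% CI for 4/16 is 7.3% to 52.4%. Over that range the 2-of-14 rule passes between 27.1% and 99.9% of the time.

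**Step 5: who is counted.** Section 7.2 speaks of fourteen relapsed or refractory patients, and the synopsis of 14 evaluable subjects. Section 7.1 excludes from efficacy only those with under 28 days of induction, who are replaced. Nothing excludes version 3 patients. Four responders over two studies means at least one study has two or more. The documents do not say which. If it is this trial and those patients count, the rule could already be met without a response on BSA-based dosing.

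**The case against.** The strongest reply is that the trial does not set out to beat 100 mg TID. The objectives in section 1 are response, its duration and progression-free survival. Section 11.2 justifies response rate as a measure of initial activity. A null representing inactive therapy is a legitimate choice for such a trial, and its lying below an earlier crenolanib rate is no contradiction. This stands, and it is why the 15% null can stay as an activity test.

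The benchmark is also weak: an interim count, pooled over two studies, with no mutation mix given, and with an interval that includes 15%. This stands too. It argues for describing the comparison, not for testing against 25% as a fixed value.

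Sections 10.3.2 and 10.3.3 do mention reporting by cohort. But they cover disposition and patient characteristics, define no cohorts, and are not carried into the efficacy analysis.

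Four stronger readings are tempting, and the documents do not support them:
- **That the protocol classes a 25% response rate as failure.** Section 8.6 limits that label to most patients, alongside low troughs and unsustained blast reductions. It does call the dose insufficient.
- **That the low null causes the 90% pass rate.** Step 3 shows that the cutoff does.
- **That the earlier rate is really 4/14 = 28.6%.** The listed outcomes (4 + 6 + 4) cover only 14 of the 16 patients, but the text does not say why, so the smaller denominator is a guess.
- **That 7 of 14 would prove improvement.** The two-sided exact 95% CI for 7/14 is 23.0% to 77.0%, which includes 25%. Set against 4/16 as data rather than a constant, the one-sided Fisher p is 0.15. The number starting on BSA-based dosing may also not be 14.

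**Conclusion.** The concern holds as a limit on what the primary test can conclude. As written, the rule passes a true 25% rate 89.9% of the time and a true 15% rate 64.3% of the time. Correcting the cutoff is needed in its own right but does not remove the point, since 5 or more of 14 still passes a 25% regimen 25.9% of the time. Rejection can support activity at most, and with the cutoff at 2 only weakly. It cannot support improvement over 100 mg TID. The unstated status of version 3 patients adds a second route by which a positive result could say little about the new dosing.

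The size rests on taking 4/16 at face value and on the CR/CRi definition in section 1.1. Section 9.1 also counts partial remission as response. On that definition the earlier rate, and so the pass probability, could only be equal or higher.

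**What to change.** In section 10.1:
- Keep the 15% null as a test of activity only.
- State that rejecting it does not show improvement over 100 mg TID.
- Replace the stated error rates with the rule's true pass probabilities: 64.3% at 15%, 89.9% at 25% and 95.3% at 30%. If the cutoff is changed, give the same three figures for the new one.
- Say whether patients enrolled under version 3 count among the 14.

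In section 10.3.7:
- Report CR+CRi separately for patients who started on BSA-based dosing and for those who started on 100 mg TID, each with its actual denominator and an exact 95% CI.
- Set these beside the section 8.6 figure as a descriptive, non-randomised comparison, with no threshold for claiming improvement.

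The cost is wording in two sections and two exact intervals, with no added patients, visits or data. The downside is a narrower claim and stated operating characteristics that look less favourable.

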10.3 Statistical and Analytical Plans

The primary end-point is overall response rate. We will use tests of the binomial proportion for both response and toxicity (Section 11). Descriptive statistics will be used for progression free survival and exploratory endpoints. Duration of response and PFS will be listed and additionally summarized using Kaplan-Meier methodology.

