10.3.1 General Considerations

Statistical analysis of this study will be the responsibility of AROG Pharmaceuticals or its designees. The clinical research physician/scientist and statistician will jointly be responsible for the appropriate conduct of an internal review process for the final study report and any study-related material to be authorized for publication by AROG or its designees.

Safety endpoints will be reported with descriptive statistics for overall study population. For continuous variables, summary statistics will include number of patients, mean, median, standard deviation, minimum, and maximum. Categorical endpoints will be summarized using number of patients, frequency, and percentages.

Any change to the data analysis methods described in the protocol will require an amendment ONLY if it changes a principal feature of the protocol. Any other change to the data analysis methods described in the protocol, and the justification for making the change, will be described in the clinical study report. Additional exploratory analyses of the data will be conducted as deemed appropriate.

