10.3.7 Efficacy Analysis

The primary end-point is overall response rate (detailed in section 9.1). Descriptive statistics will be presented for all categories of each best response category. Duration of response and PFS will be listed and additionally summarized using Kaplan-Meier methodology. In addition, if at any time unacceptable toxicity is encountered in more than 33% of patients the accrual will stop and lower doses may be investigated.

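### Section 10.1 states 85.07% power and 8.61% type I error, but the design it describes has 95.3% power and 64.3% type I error

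*Combined protocol and SAP*

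**What the plan says.** Section 10.1 (Determination of Sample Size) gives every element of a single-stage, single-arm test:

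- Null and sample size: "Therefore we will treat 15% response rate as our null hypothesis and submit 14 patients to this phase II trial".
- Decision rule: "If at least 2 patients respond to treatment, the null hypothesis will be rejected".
- Alternative and operating characteristics: "If the true response rate is 30%, this design will have 85.07% power and 8.61% type I error".

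The same section puts a one-sided 75% upper confidence bound of 10% on the response rate of D835 patients under no treatment or ineffective therapy. It then moves to the 15% null without explaining the step.

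The synopsis gives 14 evaluable subjects and section 7.2 gives fourteen patients. Section 10.3 names overall response rate as the primary endpoint and plans a binomial test for it, but gives no null value or significance level. No interim or two-stage efficacy rule is described. The only other numerical decision rule is for toxicity, in section 10.3.7 and the synopsis: "if at any time unacceptable toxicity is encountered in more than 33% of patients the accrual will stop".

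**The concern.** The inconsistency shows before any calculation. Two responders among 14 is 2/14 = 14.3%. An observed rate below 15% cannot be evidence that the true rate exceeds 15%, yet the rule rejects the null on it. Under the null the expected number of responders is 14 × 0.15 = 2.1, so a cutoff of two lies just below the expected count. A type I error near 9% is not credible for such a rule.

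This is the only efficacy decision rule with stated error rates, and it applies to the primary endpoint. An ethics board, investigator or reader who relies on the printed 8.61% would take rejection of the null as fairly strong evidence of activity. If the true type I error is far higher, that verdict says little, and the printed figure hides the fact.

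**Working it through.** **Inputs, all from section 10.1:** n = 14; null p0 = 0.15; alternative p1 = 0.30; reject if X ≥ 2. The number of responders X is taken as binomial(n, p).

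**Formula:** P(X ≥ 2) = 1 − (1 − p)^n − n·p·(1 − p)^(n−1).

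**1. Type I error, p = 0.15**

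- P(X = 0) = 0.85^14 = 0.1028
- P(X = 1) = 14 × 0.15 × 0.85^13 = 0.2539
- P(X ≥ 2) = 1 − 0.1028 − 0.2539 = **0.6433**, against the printed 0.0861. Ratio 64.33/8.61 = 7.5.

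**2. Power, p = 0.30**

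- P(X = 0) = 0.70^14 = 0.0068
- P(X = 1) = 14 × 0.30 × 0.70^13 = 0.0407
- P(X ≥ 2) = 1 − 0.0068 − 0.0407 = **0.9525**, against the printed 0.8507.

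**3. Can the printed figures be recovered another way?**

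- With the 10% bound as the null: 1 − 0.90^14 − 14 × 0.10 × 0.90^13 = 1 − 0.2288 − 0.3559 = 0.4154. Still not 0.0861.
- Solving for the rates with n = 14 and X ≥ 2: a type I error of 8.61% needs a null of about 3.5%, and power of 85.07% needs an alternative of about 22.2%. Neither rate is in the section.
- The normal approximation for X ≥ 2 gives 53.0% / 90.0% (type I error / power), or 67.3% / 94.2% with continuity correction.
- Other cutoffs at n = 14, exact:

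| Reject at | Type I error, null 15% | Type I error, null 10% | Power at 30% |
|---|---|---|---|
| ≥ 2 | 64.3% | 41.5% | 95.3% |
| ≥ 3 | 35.2% | 15.8% | 83.9% |
| ≥ 4 | 14.7% | 4.4% | 64.5% |
| ≥ 5 | 4.7% | 0.9% | 41.6% |

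No row gives the printed pair.

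**4. Which design does give the printed pair?** A search over single-stage designs, with n up to 119, all cutoffs and rates in 1% steps, found one match: n = 10, p0 = 0.05, p1 = 0.30, reject at ≥ 2.

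- Type I error: 1 − 0.95^10 − 10 × 0.05 × 0.95^9 = 1 − 0.5987 − 0.3151 = 0.0861
- Power: 1 − 0.70^10 − 10 × 0.30 × 0.70^9 = 1 − 0.0282 − 0.1211 = 0.8507

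A search of two-stage designs up to n = 60, with p1 = 30% and nulls of 5%, 10% and 15%, returned only designs equivalent to this one.

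**5. What the verdict is worth.** Rejection has probability 0.9525 at a true rate of 30% and 0.6433 at 15%. The ratio is 0.9525/0.6433 = 1.5.

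**6. Scale.** The smallest single-stage design for 15% against 30% with type I error at most 8.61% and power at least 85.07% has n = 46 and rejects at ≥ 11 (7.4% / 85.7%). That is 46 − 14 = 32 more patients.

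**The case against.** The arithmetic has no good answer. The section is intact prose with no gap, the sample size of 14 appears in three places, and no other section gives error rates or a two-stage rule. The fair objections concern consequence and remedy.

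- *The study is an open-label pilot.* There is no comparator, response categories will be reported descriptively, and nothing in the documents ties a further step to the verdict from the rule of two. This stands as a limit on the harm: the response tables keep their value. It does not excuse a stated null, rejection rule, power and type I error that disagree with one another.
- *Section 10.3 plans its own binomial test.* This stands in part, since the rule of two may not be the only inference reported. But that test has no stated null or level, so it cannot rescue the figures. It may also conflict with the rule: the exact one-sided p-value for 2/14 against 15% is 0.643.
- *Power is better than claimed.* It is higher only because the cutoff is so low, and the price is paid in false positives.
- *A new cutoff is a design choice.* This stands. The sponsor could keep the rule if its true properties were printed and it were presented as a weak screen. Nor need the protocol print the size of a trial it is not running.
- *A 5% null has no support in the documents.* This stands. It appears here only because it reproduces the printed pair, and carry-over from another design is an inference.

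**Conclusion.** The concern holds. For the design in section 10.1 the type I error is 64.3%, not 8.61%, and the power at a 30% true rate is 95.3%, not 85.07%. The result assumes only 14 evaluable patients, independent responses and a single look, as the documents describe. It does not depend on the choice of exact or approximate method, and taking the 10% bound as the null still leaves 41.5%. As written, the rule does not control false positives, and its verdict is only about 1.5 times as likely under a 30% response rate as under 15%. This is an error in the primary-endpoint design and must be corrected.

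**What to change.** **Minimum.** In section 10.1, replace the printed figures with 64.3% type I error and 95.3% power, and say that the rule is a low-bar screen that does not control false positives. This is a change of wording.

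**Better.** Keep 14 patients, state one null with its reason, including why the text moves from a 10% bound to 15%, and give a matching cutoff with exact error rates. Options that use the nulls in the section:

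- 15% null, ≥ 4 responders: 14.7% type I error, 64.5% power at 30%.
- 15% null, ≥ 5 responders: 4.7% type I error, 41.6% power at 30% and 72.1% at 40%.
- 10% null, ≥ 4 responders: 4.4% type I error, 64.5% power at 30%.

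The null and level of the binomial test in section 10.3 should be stated to agree with whichever rule is kept.

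**Cost.** No extra patients, but the stated power falls. Under section 10.3.1 a change to the analysis methods "will require an amendment ONLY if it changes a principal feature of the protocol"; a new null or cutoff for the primary endpoint probably qualifies. Section 8.6 already reports four CR/CRi among 16 patients across two studies at the earlier flat dose, and does not say how many belong to this trial or count towards the 14. Any new cutoff should therefore be justified without reference to those responses. Enlarging the trial to 46 patients is not asked for.

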10.2 Toxicity Evaluation

Crenolanib has been well tolerated in studies including over 100 patients and toxicity patterns are relatively well understood.

10.3 Statistical and Analytical Plans

The primary end-point is overall response rate. We will use tests of the binomial proportion for both response and toxicity (Section 11). Descriptive statistics will be used for progression free survival and exploratory endpoints. Duration of response and PFS will be listed and additionally summarized using Kaplan-Meier methodology.

10.3.1 General Considerations

Statistical analysis of this study will be the responsibility of AROG Pharmaceuticals or its designees. The clinical research physician/scientist and statistician will jointly be responsible for the appropriate conduct of an internal review process for the final study report and any study-related material to be authorized for publication by AROG or its designees.

Safety endpoints will be reported with descriptive statistics for overall study population. For continuous variables, summary statistics will include number of patients, mean, median, standard deviation, minimum, and maximum. Categorical endpoints will be summarized using number of patients, frequency, and percentages.

Any change to the data analysis methods described in the protocol will require an amendment ONLY if it changes a principal feature of the protocol. Any other change to the data analysis methods described in the protocol, and the justification for making the change, will be described in the clinical study report. Additional exploratory analyses of the data will be conducted as deemed appropriate.

10.3.2 Patient Disposition

A detailed description of patient disposition, broken by cohort, will be provided. It will include:

• Summary of patients entered

- Total number of patients entered
- Total number of patients enrolled
- Summary of reasons for patients entered, but not enrolled
- Summary of reasons for patient discontinuation from study treatment
- Summary of all identified important protocol violations

10.3.3 Patient Characteristics

Patient characteristics will be reported for each cohort, and include a summary of the following:

- Patient demographics
- Baseline disease characteristics
- Pre-existing conditions
- Prior therapies

Other patient characteristics will be summarized as deemed appropriate.

10.3.4 Concomitant Therapy

Concomitant medication will be reported overall as well as summarized in a frequency table using the terms recorded on the CRF. If warranted, an attempt may be made to determine how concomitant medications are related to observed study outcomes.

10.3.5 Treatment Compliance

Treatment compliance information will be collected through pill counts at each tumor assessment visit and also by analyzing patient diaries where patients will record their daily drug intake. The estimate of percent compliance will be given by:

The number of tablets taken will be determined by counting the number of tablets returned at each visit and subtracting that number from the number of tablets dispensed. The number of tablets expected to be taken will be determined by the assigned dose and taking into account any prescribed dose reductions and omissions.

No minimal level of compliance will be defined for patient inclusion in efficacy analyses. An exploratory analysis of compliance may be performed by regressing percent compliance on selected efficacy endpoints. If significant results are indicated, analysis may be performed to determine the level of compliance that best delineates each endpoint

